#### **8.2.4.1.1. Adverse Events Identified as Incyte MedDRA Queries**

Prospectively defined Incyte MedDRA Queries will be used to conduct analyses to evaluate the safety profile. Incyte MedDRA Queries are queries constructed by Incyte based on MedDRA preferred terms identified through review of standardized MedDRA queries for clinically relevant terms. Sets of included terms will be identified and archived before database lock for the individual studies. Incyte MedDRA Queries searches are to be conducted for the following TEAEs: hemorrhage events, dizziness, weight gain, thrombotic events, urinary tract infections, herpes zoster infections, tuberculosis, hepatitis B reactivation, and infections other than those stated previously. In addition, these other infections will be analyzed by subcategories of upper respiratory tract infections, lower respiratory tract infections, skin and soft tissue infections, alimentary tract infections, other viral infections, and miscellaneous infections with each tabulated by MedDRA preferred term.

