1.4. Potential Risks and Benefits of the Combination Regimens

The principle toxicities of administering agents that modulate the immune system are irAEs including skin manifestations, pneumonitis, enterocolitis, and endocrinopathies. Immune-related AEs have been reported in subjects treated with nivolumab and ipilimumab. As the use of immunotherapies become more prevalent, guidelines for the management of irAEs continue to evolve. Careful monitoring, early diagnosis, and treatment with corticosteroids for more severe events is recommended. The time of onset of irAEs varies, with skin manifestations and GI toxicity seen early and elevated liver enzymes and endocrinopathies appearing later

(Weber et al 2015). Subjects enrolled in this study will be carefully monitored for the onset of irAEs, and guidelines for the management of these toxicities are provided in the Protocol and in the prescribing information for nivolumab and ipilimumab.

[REDACTED]

[REDACTED]

[REDACTED]

[REDACTED]

[REDACTED]

[REDACTED]

[REDACTED]

[REDACTED]

[REDACTED]

[REDACTED]

[REDACTED]

[REDACTED]

[REDACTED]

[REDACTED]

[REDACTED]

[REDACTED]

[REDACTED]

[REDACTED]

[REDACTED]

[REDACTED]

[REDACTED]

[REDACTED]

[REDACTED]

[REDACTED]

[REDACTED]

[REDACTED]

[REDACTED]

[REDACTED]

[REDACTED]

[REDACTED]

[REDACTED]

[REDACTED]

[REDACTED]

[REDACTED]

[REDACTED]

[REDACTED]

[REDACTED]

[REDACTED]

[REDACTED]

[REDACTED]

[REDACTED]

[REDACTED]

[REDACTED]

[REDACTED]

[REDACTED]

[REDACTED]

[REDACTED]

[REDACTED]

[REDACTED]

[REDACTED]

[REDACTED]

[REDACTED]

- [REDACTED]
- [REDACTED]
- [REDACTED]
- [REDACTED]

[REDACTED]

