^c As of Protocol Amendment 5, the safety follow-up visits will include AE and concomitant medication assessment only and may be completed remotely (such as by televisit).

- ^d As of Protocol Amendment 5, no further survival follow-up assessment will be required beyond the last safety follow-up visit.
- ^e Evaluation window only applies to Cycle 6 Day 1.
- ^f In Treatment Group B, INCAGN01876 is only administered on Day 1 of Cycles 1 and 2.
- ^g In Treatment Groups B, E, H, and L, nivolumab administration begins at Cycle 3 Day 1.
- ^h For subjects enrolled into Treatment Groups C and C2 (INCAGN01876 + ipilimumab) and Treatment Groups D and J (INCAGN01876 + nivolumab + ipilimumab), ipilimumab will be administered on Cycle 1 Day 1 and then Day 1 of every 3rd cycle (Cycle 1, Cycle 4, Cycle 7, etc). In Treatment Groups E and L ipilimumab administration begins at Cycle 3 Day 1 and then continues on Day 1 of every third cycle. If higher doses of ipilimumab are tested (eg, 3 mg/kg every 3 weeks [21 days] for 4 doses), then ipilimumab will be administered on Day 1 of each 3-week (21-day) cycle for a total of 4 doses. If the scheduled ipilimumab doses fall on days other than Day 1 of a cycle, the subjects will need to be present in clinic for the infusion, and any standard procedures required by the site should be performed.
- ⁱ Applicable to all subjects at Cycle 1 Day 8. At Cycle 6 Day 8, only required if subject is experiencing AEs > Grade 2.
- ^j All 12-lead ECGs will be performed with the subject in a recumbent or semirecumbent position after 5 minutes of rest and should not be performed within 15 minutes after a blood collection. ECGs will be collected at screening and at least every 8 weeks, or as clinically indicated per prescribing instructions for nivolumab, as well as the EOT and first safety follow-up visits.
- ^k The initial tumor imaging will be performed within 28 days before the first dose of study treatment. Images of the chest, abdomen, and pelvis are required for all subjects. Scans performed as part of routine clinical management are acceptable for use as the screening scan if they are of diagnostic quality and performed within 28 days before the first dose of study treatment. The same imaging technique should be used for a subject throughout the study. Local reading (investigator assessment with site radiology reading) will be used to determine eligibility and for subject management.

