#### 8.4. Vital Signs

Values at each scheduled visit, change, and percentage change from baseline for vital signs, including systolic blood pressure, diastolic blood pressure, pulse, respiration rate, and body temperature will be summarized descriptively.

Criteria for clinically notable vital sign abnormalities are defined in Table 9. The abnormal values for subjects exhibiting clinically notable vital sign abnormalities will be listed along with their assigned treatment group. Alert vital signs are defined as an absolute value outside the defined range and percentage change > 25%. The abnormal values for subjects exhibiting alert vital sign abnormalities will be listed.

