### 8.5. Electrocardiograms

Twelve-lead ECGs including heart rate, PR, QRS, QT, QTcF, QTcB, JTc, and RR intervals will be obtained for each subject at the screening, end of treatment, and safety follow-up visits during the study. Values at each scheduled visit, change, and percentage change from baseline will be summarized for each ECG parameter. Baseline will be determined as the average of all nonmissing values before the first administration of INCAGN01876, nivolumab, or ipilimumab.

Criteria for clinically notable ECG abnormalities are defined in [Table 10](#). Subjects exhibiting clinically notable ECG abnormalities will be listed with study visit and assigned treatment group. Abnormal values for subjects with alert ECG values, defined as both the absolute value and the percentage change from baseline being outside normal ranges, will be identified and listed.

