## Figures

Figure No.	Title	Population
4.1 Efficacy		
4.1.1	Kaplan-Meier Estimates of Progression-Free Survival	Phase 2 FAS Population
4.1.2	Kaplan-Meier Estimates of Overall Survival	Phase 2 FAS Population
4.1.3.1	Swim Plot of Duration of Response - by Treatment Group	Phase 1 FAS Population
4.1.3.2	Swim Plot of Duration of Response - by Treatment Group and Tumor Type	Phase 2 FAS Population
4.1.4.1	Waterfall Plot of Percentage Change From Baseline in Sum of Target Lesions - by Treatment Group and Dose	Phase 1 FAS Population
4.1.4.2	Waterfall Plot of Percentage Change From Baseline in Sum of Target Lesions - by Treatment Group and Tumor Type	Phase 2 FAS Population
4.1.5.1	Spider Plot of Percentage Change From Baseline in Sum of Target Lesions - by Treatment Group	Phase 1 FAS Population
4.1.5.2	Spider Plot of Percentage Change From Baseline in Sum of Target Lesions - by Treatment Group and Tumor Type	Phase 2 FAS Population
4.90 Safety Data		
4.90.1.1	Bar Chart for Incidence of Treatment Emergent Adverse Events of Special Interest - by Treatment Group and Dose	Phase 1 FAS Population
4.90.1.2	Bar Chart for Incidence of Treatment Emergent Adverse Events of Special Interest - by Treatment Group and Tumor Type	Phase 2 FAS Population
4.90.2.1	Line Graph of Selected Laboratory Values by Study Visit	Phase 1 FAS Population
4.90.2.2	Line Graph of Selected Laboratory Values by Study Visit	Phase 2 FAS Population
4.90.3.1	Box-and-Whisker Plot of Selected Laboratory Values by Study Visit	Phase 1 FAS Population
4.90.3.1	Box-and-Whisker Plot of Selected Laboratory Values by Study Visit	Phase 2 FAS Population

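### The SAP's prespecified MedDRA queries cover none of the protocol's immune-toxicity categories, and its ECG visit list and temperature alert rule also need correcting

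*SAP*

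**What the plan says.** **Queries.** SAP 8.2.4.1.1 is a subsection of 8.2.4.1 (irAEs). It names nine topics: "hemorrhage events, dizziness, weight gain, thrombotic events, urinary tract infections, herpes zoster infections, tuberculosis, hepatitis B reactivation", and a ninth group for all other infections. Their terms are fixed in advance: "Sets of included terms will be identified and archived before database lock for the individual studies".

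**Named toxicities.** Protocol 1.4 states: "The principle toxicities of administering agents that modulate the immune system are irAEs including skin manifestations, pneumonitis, enterocolitis, and endocrinopathies". Protocol Appendix B gives management guidance for seven irAE categories. Protocol Table 6 and Section 5.4.9 treat an ocular irAE of Grade 2 or higher as a DLT and as unacceptable toxicity.

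**Other irAE displays.** SAP 8.2.4.1 has the medical monitor and clinical scientist review terms periodically, without regard to treatment group, and allows this after database lock. SAP 8.2.5 and Tables 3.2.16 to 3.2.19 tabulate irAEs by SOC and PT. Appendix A also plans Figure 4.90.1.1, "Bar Chart for Incidence of Treatment Emergent Adverse Events of Special Interest - by Treatment Group and Dose", with a Phase 2 counterpart.

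**ECG.** SAP 8.5 says ECGs are obtained "at the screening, end of treatment, and safety follow-up visits during the study". Protocol Table 10, footnote j, says "ECGs will be collected at screening and at least every 8 weeks", in addition to end of treatment and the first safety follow-up visit.

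**Alerts.** SAP 8.4: "Alert vital signs are defined as an absolute value outside the defined range and percentage change > 25" percent.

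**The concern.** Safety and tolerability is a primary endpoint (SAP 2.3.1), and the DMC is to review irAE rates by treatment group (SAP 9.1.1). Both uses need a stable definition of each immune toxicity. The only grouped-term analysis in the AE section whose terms are fixed before lock is the query list, and it does not address the toxicities that the protocol puts first. In an open-label study, a term set that can be settled after lock is open to the criticism that it was shaped by the data.

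The other two items are smaller. The ECG visit list does not match the protocol version the SAP says it is based on, so a programmer could reasonably leave the on-treatment ECGs out of the by-visit summaries. The alert rule for vital signs has a condition that one of its five parameters cannot meet.

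**Working it through.** The plan states no figure on this point that could be reproduced. The check compares texts, with simple arithmetic for the ECG count and the alert rule.

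**1. Query topics against named irAEs**

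| Category (Protocol Appendix B, plus ocular from Table 6) | Covered by a topic in SAP 8.2.4.1.1? |
|---|---|
| Pneumonitis | No (lower respiratory infection is a different event) |
| Diarrhea/colitis | No (alimentary tract infection is a different event) |
| Hepatitis | No (hepatitis B reactivation is viral) |
| Dermatitis | No (skin infection is a different event) |
| Renal failure/nephritis | No |
| Endocrinopathies | No |
| Neuropathies | No |
| Ocular irAE | No |

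Result: 0 of 7 Appendix B categories, no ocular irAE, and 0 of the 4 toxicities named in Protocol 1.4.

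**2. What the irAE tables supply instead**

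| Display | Investigator-identified | Sponsor-identified |
|---|---|---|
| Any grade, SOC and PT | Table 3.2.16 | Table 3.2.17 |
| Maximum severity | Table 3.2.18 | none |
| Grade 3 or higher | Table 3.2.19 | none |

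SAP 8.2.4.1 itself expects investigator flags to be incomplete: its example is a rash counted as an irAE although the investigator did not report it as one. A Grade 3 event recognized only by the sponsor would appear in Table 3.2.17 without its grade and would be absent from Table 3.2.19.

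Now take a syndrome coded in two SOCs, such as immune hepatitis recorded as a hepatic diagnosis in some subjects and as raised liver tests in others. Let a and b be the proportions of subjects in the two SOCs. The largest row attributable to the syndrome is max(a, b). The category rate lies between max(a, b), if the same subjects have both, and a + b, if they are different subjects. Since a + b ≤ 2 × max(a, b), the category rate can be up to twice the largest row, and the planned tables do not show where in that range it falls.

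**3. ECGs not named in SAP 8.5**

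- SAP 2.1 and 3.5 give Protocol Amendment 2 (22 AUG 2017) as the base. Protocol Appendix C shows that this amendment introduced the 8-weekly ECG. The mismatch therefore does not come from a later amendment.
- At the current protocol's 24-month treatment maximum: 104 weeks / 8 = 13 on-treatment ECGs.
- Over 12 months: 52 / 8 = 6.5, that is 6.

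**4. Alert rule**

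An alert needs a value outside the SAP Table 9 range and a change above 25%.

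- Temperature from an assumed baseline of 36.8 °C: 36.8 × 1.25 = 46.0 °C and 36.8 × 0.75 = 27.6 °C. From 37 °C: 46.25 °C and 27.75 °C.
- In reverse, a value of 38 °C is a 25% rise only from 38 / 1.25 = 30.4 °C, and 35.5 °C is a 25% fall only from 35.5 / 0.75 = 47.3 °C.
- For comparison, the two conditions coincide at ordinary baselines for systolic pressure (155 / 1.25 = 124 mmHg) and pulse (100 / 1.25 = 80 bpm). The rule can work there and fails for temperature.

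**The case against.** The strongest reply is that little is lost, and much of it stands.

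- *A reader might infer that the SAP ignores irAEs or shows them only by PT.* It does neither. Tables 3.2.16 to 3.2.19 have SOC rows, and Listings 2.6.9 and 2.6.10 give the events. With assumed rates of 4% colitis, 3% enterocolitis and 5% diarrhea in different subjects, the gastrointestinal SOC row would show 4 + 3 + 5 = 12%. Splitting within one SOC is not the problem. The gap concerns syndromes that cross SOCs, a term set not fixed before lock, and missing severity tables for sponsor-identified events.
- *A reader might infer that the listed queries are irrelevant and should be replaced.* Hepatitis B reactivation is the subject of exclusion criterion 14, and infection under steroids or infliximab is raised in Appendix B. The list is incomplete, not misplaced.
- *A reader might infer that on-treatment ECGs are excluded.* SAP 3.5 defers to the protocol for schedules, and SAP 8.5 goes on to summarize each scheduled visit. The three-visit sentence conflicts with that wording but does not exclude the data. Thirteen ECGs is also a near-maximum, because Protocol 4.4 expects participation, including follow-up, to average 12 to 18 months.
- *A reader might infer that fever, or on-treatment data in general, is lost from the alert displays.* The alert rules have no timing restriction, and temperatures above 38 °C are listed as clinically notable with no change condition.

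Figure 4.90.1 may be meant to show irAEs, since they come first under SAP 8.2.4. That section also holds the query topics and infusion reactions, and the SAP does not say which are plotted.

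**Conclusion.** The point holds in a limited form.

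- **Main item.** No prespecified query group covers any of the 7 Appendix B categories or ocular irAEs. The existing irAE tables do not fill the gap, because their term set may be settled after lock and their severity versions omit sponsor-identified events. The numerical effect on any category rate cannot be stated from the documents, since it depends on how events are coded. For a syndrome split over two SOCs, the bound is a factor of two.
- **ECG.** The SAP conflicts with its own base protocol and leaves it unclear whether up to 13 on-treatment ECGs per subject enter the by-visit summaries. No loss of data is shown.
- **Temperature alert.** The rule cannot realistically be met. The consequence is confined to the alert listing.

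The protocol's analysis sections on vital signs and ECGs (9.4.2.3 and 9.4.2.4) appear in its table of contents but not in the text available for this review, so they could not be checked. These corrections should be made because safety is a primary endpoint, but none of them undermines the safety analysis as a whole.

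**What to change.** 1. In SAP 8.2.4.1.1, keep the present queries and add groups for pneumonitis, diarrhea/colitis, hepatitis, dermatitis, renal failure/nephritis, endocrinopathies, neuropathies and ocular events, with terms archived before database lock.
2. Report each group at any grade and at Grade 3 or higher, including sponsor-identified irAEs. State that Figure 4.90.1 plots these groups.
3. In SAP 8.5, add the 8-weekly on-treatment visits so that the visit list agrees with Protocol Amendment 2, and add a summary of the worst on-treatment value.
4. In SAP 8.4, define the temperature alert by an absolute change from baseline, with the size set by the sponsor, and keep the percentage rule for the other parameters.

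The cost is a term list, a few more outputs and edits to two SAP sections. No new data are needed. Appendix A already allows changes to the table and figure list that do not affect the nature of the analysis without a SAP amendment. The new query groups and the alert definition are better written into the SAP text.

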#### **8.2.4.2. Infusion-Related Reactions**

Infusion-related reactions, defined as AEs that are identified as infusion-related reaction by the investigator on the infusion-related reaction case report form, will be summarized in a table and listing. The summaries will include the treatment group, dose level, cycle number, study day, date of onset of AE, date of the associated infusion, and signs and symptoms of the infusion-related reaction.

## **8.2.5. Adverse Event Summaries**

An overall summary of AEs by treatment group and by tumor type as applicable will include the following:

- Number (%) of subjects reporting any TEAEs
- Number (%) of subjects reporting any DLTs
- Number (%) of subjects reporting any SAEs
- Number (%) of subjects reporting any Grade 3 or 4 TEAEs

- Number (%) of subjects reporting any TEAEs related to INCAGN01876
- Number (%) of subjects reporting any TEAEs related to nivolumab
- Number (%) of subjects reporting any TEAEs related to ipilimumab
- Number (%) of subjects who temporarily interrupted INCAGN01876 because of TEAEs
- Number (%) of subjects who temporarily interrupted nivolumab because of TEAEs
- Number (%) of subjects who temporarily interrupted ipilimumab because of TEAEs
- Number (%) of subjects who permanently discontinued INCAGN01876 because of TEAEs
- Number (%) of subjects who permanently discontinued nivolumab because of TEAEs
- Number (%) of subjects who permanently discontinued ipilimumab because of TEAEs
- Number (%) of subjects with INCAGN01876 dose reductions because of TEAEs
- Number (%) of subjects who had a fatal TEAE
- Number (%) of subjects who withdrew from study because of a TEAE

The following summaries will be produced by MedDRA term:

- Summary of TEAEs by SOC and PT
- Summary of TEAEs by PT in decreasing order of frequency
- Summary of TEAEs by SOC, PT, and maximum severity
- Summary of Grade 3 or higher TEAEs by SOC and PT
- Summary of INCAGN01876 treatment-related AEs by SOC and PT
- Summary of nivolumab treatment-related AEs by SOC and PT
- Summary of ipilimumab treatment-related AEs by SOC and PT
- Summary of Grade 3 or higher INCAGN01876 treatment-related AEs by SOC and PT
- Summary of Grade 3 or higher nivolumab treatment-related AEs by SOC and PT
- Summary of Grade 3 or higher ipilimumab treatment-related AEs by SOC and PT
- Summary of INCAGN01876 treatment-related AEs with a fatal outcome by SOC and PT
- Summary of nivolumab treatment-related AEs with a fatal outcome by SOC and PT
- Summary of ipilimumab treatment-related AEs with a fatal outcome by SOC and PT
- Summary of treatment-emergent SAEs by SOC and PT
- Summary of treatment-emergent SAEs by PT in descending order of frequency

- Summary of INCAGN01876 treatment-related SAEs by SOC and PT
- Summary of nivolumab treatment-related SAEs by SOC and PT
- Summary of ipilimumab treatment-related SAEs by SOC and PT
- Summary of treatment-emergent non-SAE by SOC and PT.
- Summary of TEAEs leading to INCAGN01876 dose reduction by SOC and PT
- Summary of TEAEs leading to any dose interruption by SOC and PT
- Summary of TEAEs leading to discontinuation of INCAGN01876 by SOC and PT
- Summary of treatment-emergent irAEs (investigator identified) by SOC and PT
- Summary of treatment-emergent irAEs (sponsor identified) by SOC and PT
- Summary of treatment-emergent irAEs (investigator identified) by SOC, PT, and maximum severity
- Summary of Grade 3 or higher treatment-emergent irAEs (investigator identified) by SOC and PT
- Life table estimate of time to first Grade 3 or higher TEAEs
- Summary of TEAEs leading to death by SOC and PT
- Summary of infusion reactions

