5.2. Study Drugs

5.2.1. INCAGN01876

5.2.1.1. Description and Administration

The study drug (INCAGN01876) is supplied as a sterile, single-use solution for injection, in a 10 mL glass vial. Each vial contains 50 mg of INCAGN01876 in 5 mL at a concentration of 10 mg/mL in [REDACTED], and pH [REDACTED]. The infusion site should not be used for blood sampling.

Study drug will be diluted in [REDACTED] or acceptable admixture as outlined in the Pharmacy Manual and will be administered by qualified site personnel as an IV infusion over a 30-minute (-5/+10 minutes) period on Day 1 of each cycle when INCAGN01876 is scheduled to be given. On days when INCAGN01876 will be administered along with other agents administered by infusion, INCAGN01876 will be administered first, followed by a 30-minute wait before administration of the subsequent immune therapy/therapies.

In Phase 1, subjects will be administered study drug, according to cohort enrollment (see [Table 2](#)), Q2W (14-day cycles), in combination with immune therapies. In Phase 2, subjects will be administered study drug at the recommended dose Q2W (14-day cycles), in combination with immune therapies. In Treatment Group B, INCAGN01876 is only administered on Day 1 of Cycles 1 and 2.

Subjects will continue to receive INCAGN01876 as long as they are deriving benefit and have not met any of the Protocol-defined conditions for treatment withdrawal (see Section [5.5](#)), or for up to 24 months from the first dose of study treatment, whichever occurs first.

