3.2.15.1	Summary of Treatment-Emergent Adverse Events Leading to Discontinuation of INCAGN01876 by MedDRA System Organ Class and Preferred Term - by Treatment Group and Dose	Phase 1 FAS Population	X	
3.2.15.2	Summary of Treatment-Emergent Adverse Events Leading to Discontinuation of INCAGN01876 by MedDRA System Organ Class and Preferred Term - by Treatment Group and Tumor Type	Phase 2 FAS Population	X	
3.2.16.1	Summary of Treatment-Emergent Immune-Related Adverse Events (Investigator Identified) by MedDRA System Organ Class and Preferred Term - by Treatment Group and Dose	Phase 1 FAS Population	X	
3.2.16.2	Summary of Treatment-Emergent Immune-Related Adverse Events (Investigator Identified) by MedDRA System Organ Class and Preferred Term - by Treatment Group and Tumor Type	Phase 2 FAS Population	X	
3.2.17.1	Summary of Treatment-Emergent Immune-Related Adverse Events (Sponsor Identified) by MedDRA System Organ Class and Preferred Term - by Treatment Group and Dose	Phase 1 FAS Population	X	
3.2.17.2	Summary of Treatment-Emergent Immune-Related Adverse Events (Sponsor Identified) by MedDRA System Organ Class and Preferred Term - by Treatment Group and Tumor Type	Phase 2 FAS Population	X	
3.2.18.1	Summary of Treatment-Emergent Immune-Related Adverse Events (Investigator Identified) by MedDRA System Organ Class, Preferred Term, and Maximum Severity - by Treatment Group and Dose	Phase 1 FAS Population	X	
3.2.18.2	Summary of Treatment-Emergent Immune-Related Adverse Events (Investigator Identified) by MedDRA System Organ Class, Preferred Term, and Maximum Severity - by Treatment Group and Tumor Type	Phase 2 FAS Population	X	

Table No.	Title	Population	Standard	In-Text
3.2.19.1	Summary of Grade 3 or Higher Treatment-Emergent Immune-Related Adverse Events (Investigator Identified) by MedDRA System Organ Class and Preferred Term - by Treatment Group and Dose	Phase 1 FAS Population	X	X
3.2.19.2	Summary of Grade 3 or Higher Treatment-Emergent Immune-Related Adverse Events (Investigator Identified) by MedDRA System Organ Class and Preferred Term - by Treatment Group and Tumor Type	Phase 2 FAS Population	X	X
3.2.20	Life Table Estimate of Time to First Grade 3 or Higher Treatment-Emergent Adverse Event - by Treatment Group and Tumor Type	Phase 2 FAS Population	X	
3.2.21.1	Summary of Adverse Events With a Fatal Outcome by System Organ Class and Preferred Term - by Treatment Group and Dose	Phase 1 FAS Population	X	

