## Listings

Listing No.	Title
2.1 Discontinued Subjects (Subject Disposition)	
2.1.1	Subject Enrollment and Disposition Status
2.1.2	Subject Inclusion and Exclusion Criteria Violations
2.2 Protocol Deviation	
2.2.1	Protocol Deviations and Violations
2.3 Data Excluded From [REDACTED] Efficacy, and/or Safety Analyses	
2.3.1	Analysis Population
2.4 Demography and Baseline (Including Prior and Concomitant Medications)	
2.4.1	Demographic
2.4.2.1	Baseline Disease Characteristics for Phase 1 Solid Tumor Types
2.4.2.2	Baseline Disease Characteristics for Phase 2 – by Tumor Type

Listing No.	Title
2.4.3	Disease History
2.4.4	Prior Radiation Treatment
2.4.5	Prior Systemic Therapy
2.4.6	Prior Surgery or Surgical Procedure
2.4.7	Medical History
2.4.8	Prior and Concomitant Medication
2.5 Efficacy	
2.5.1.1	Best Overall Response With Confirmed CRs and PRs Under RECIST v1.1
2.5.1.2	Best Overall Response With Unconfirmed CRs and PRs Under RECIST v1.1
2.5.2.1	Best Overall Response With Confirmed CRs and PRs Under mRECIST v1.1
2.5.2.2	Best Overall Response With Unconfirmed CRs and PRs Under mRECIST v1.1
2.5.3	Overall Response Assessment
2.5.4	Response Assessment: Target Lesions
2.5.5	Response Assessment: Non-Target Lesions
2.5.6	Response Assessment: New Lesions
2.5.7	ECOG status
2.6 Adverse Events (and Exposure)	
2.6.1.1	Study Drug Administration for INCAGN01876
2.6.1.2	Study Treatment Administration for Nivolumab
2.6.1.3	Study Treatment Administration for Ipilimumab
2.6.2	Adverse Events
2.6.3	Dose-Limiting Toxicities
2.6.4	Serious Adverse Events
2.6.6	Fatal Adverse Events
2.6.8	Adverse Events Leading to Discontinuation of INCAGN01876
2.6.9	Investigator-Identified Immune-Related Adverse Events
2.6.10	Sponsor-Identified Immune-Related Adverse Events
2.6.11	Infusion Reactions
2.7 Laboratory Data	
2.7.1	Clinical Laboratory Values - Hematology
2.7.2	Clinical Laboratory Values - Chemistry
2.7.3	Abnormal Clinical Laboratory Values
2.8 Vital Signs	
2.8.1	Vital Signs
2.8.2	Abnormal Vital Sign Values
2.8.3	Alert Vital Sign Values
2.9 ECG	
2.9.1	12-Lead Local ECG Values
2.9.2	Abnormal 12-Lead Local ECG Values
2.9.3	Alert 12-Lead Local ECG Values
2.10 Physical Examination	
2.10.1	Body Weight

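### The SAP links adverse event terms to stopping treatment only for INCAGN01876, so in Group B the by-term table and listing do not cover toxicity stops during the nivolumab phase

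*SAP*

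**What the plan says.** SAP Section 8.2.5 has two layers of discontinuation reporting.

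- The overall adverse event summary counts subjects for each agent separately. There is a row for INCAGN01876 and two more: "Number (%) of subjects who permanently discontinued nivolumab because of TEAEs" and "Number (%) of subjects who permanently discontinued ipilimumab because of TEAEs". No row covers any study treatment.
- The breakdown by system organ class (SOC) and preferred term (PT) exists for one agent only: "Summary of TEAEs leading to discontinuation of INCAGN01876 by SOC and PT".

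Appendix A follows the second layer. Table 3.2.15.1 is titled "Summary of Treatment-Emergent Adverse Events Leading to Discontinuation of INCAGN01876 by MedDRA System Organ Class and Preferred Term - by Treatment Group and Dose", and Table 3.2.15.2 is its Phase 2 counterpart. The only listing devoted to these events, 2.6.8, is "Adverse Events Leading to Discontinuation of INCAGN01876".

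The neighbouring summary of interruptions has no such restriction: "Summary of TEAEs leading to any dose interruption by SOC and PT".

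On dosing, Protocol Section 5.2.1.1 states: "In Treatment Group B, INCAGN01876 is only administered on Day 1 of Cycles 1 and 2". Section 5.2.2.1 starts nivolumab at Cycle 3 Day 1 in Group B and allows it for up to 24 months from the first dose of study treatment. Section 5.5.1 requires all study treatments to stop when any one of them is permanently stopped.

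**The concern.** Safety and tolerability form a primary endpoint, and a table of the toxicities that ended treatment is one of the main tolerability displays. In the concurrent groups the restriction to INCAGN01876 does little harm: all drugs stop together, so stopping INCAGN01876 stands in for stopping treatment. That stand-in fails where INCAGN01876 is a short run-in. Once the second dose has been given, no INCAGN01876 remains to be discontinued, so a toxicity that ends treatment later ends nivolumab.

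The same table would then describe different treatment periods in different columns: the whole of treatment in Group A, and little more than the run-in in Group B. A reader who wants to know which toxicities ended treatment on the sequenced schedule would not find the answer there.

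**Working it through.** The plan gives no figure to reproduce. The check compares the scope of the planned displays with the Group B schedule.

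**1. Group B timeline** (14-day cycles; Protocol Sections 5.2.1.1, 5.2.2.1 and 5.4.2)

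- INCAGN01876: Day 1 and Day 1 + 14 = Day 15.
- First nivolumab dose, Cycle 3 Day 1: 1 + 2 × 14 = Day 29.
- DLT window: Day 29 to Day 56. It lies wholly after the last INCAGN01876 dose.
- Longest treatment: 24 months, about 730 days; 730 / 14 ≈ 52 cycles. INCAGN01876 is scheduled in 2 of them, so up to 52 − 2 = 50 are nivolumab only.

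**2. Where a TEAE that stops nivolumab from Cycle 3 on would appear**

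| Display | Scope | Shows the event? | Links the term to the stop? |
|---|---|---|---|
| Overall AE summary (8.2.5; Table 3.2.1.1) | Count for each agent | Yes, as a nivolumab count by treatment group and dose | No |
| TEAE tables by SOC/PT | All TEAEs | Yes, by term | No |
| Nivolumab-related, Grade 3 or higher, serious and immune-related tables | By attribute | Where applicable, by term | No |
| Listing 2.6.2 | All AEs | Yes | Not a dedicated display of stops |
| Disposition (6.2) | Primary reason for stopping | Yes, as a reason | No AE term |
| Table 3.2.15.1, Listing 2.6.8 | Discontinuation of INCAGN01876 | Not as defined | Would have been the link |

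**3. How far DLT reporting fills the gap**

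Protocol Table 6 makes it a DLT if toxicity of any grade prevents the planned number of doses within the 28-day period, and SAP Section 8.2.2 lists DLTs by type, dose level and treatment group. In Group B the nivolumab doses inside the window fall on Day 29 and Day 29 + 14 = Day 43; the next, Day 43 + 14 = Day 57, is outside it. A toxicity that prevents the Day 43 dose is therefore a DLT and is listed. One that leads to stopping after the Day 43 dose is a DLT only if it meets another criterion, and stops after Day 56 are outside the planned window.

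**4. Which groups are affected**

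- As the SAP is written (Section 5.2, based on Protocol Amendment 2): Groups B, E, G and K are all run-in only.
- Under the current protocol: G and K are gone from Table 5, and Table 4 has Group E continuing INCAGN01876 alongside the other drugs. The remaining sequenced groups, H and L, also continue it. Group B is the only one left, and no current Phase 2 group is affected.

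**5. Is the narrow scope the SAP's usual practice?**

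No. Interruptions are tabulated for any drug. Treatment-related AEs, related Grade 3 or higher AEs, related fatal AEs and related SAEs are each tabulated by SOC and PT for all three agents. Among these by-term displays, discontinuation and dose reduction are the ones narrowed to INCAGN01876, and the protocol allows no dose reductions for toxicity.

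**The case against.** The strongest reply is that little is lost. The overall summary is an in-text table and shows nivolumab stops by treatment group and dose, so Group B's count stands beside Group A's. Table 3.2.15.1 is not an in-text table. The terms appear in the TEAE tables and in Listing 2.6.2, and early stops may be listed as DLTs. Protocol Section 9.4.2.1 asks only for tabulated incidence of AEs and treatment-related AEs, and Appendix A calls its own list a guideline. All of this stands. It limits the gap to one cross-classification, term by discontinuation.

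The gap also depends on site coding. Because Section 5.5.1 has all treatments discontinued together, a site might record INCAGN01876 as withdrawn even after its course is complete, and the event would then enter the table. The case report form is not available here and the SAP gives no rule, so this cannot be settled. It does mean that the table's content in Group B would rest on coding habits.

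Three stronger readings are tempting, and the documents do not support them.

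- *Toxicity stops in Group B would be invisible.* They would not; step 2 of the check shows where they appear.
- *The sequenced schedule would be reported as better tolerated.* The in-text count by group works against that. The supportable statement is that the columns of one table cover different treatment periods.
- *The number of missing events can be estimated from the discontinuation rates in Protocol Section 1.3.2.2.* Those rates are for nivolumab plus ipilimumab, and Group B receives no ipilimumab. Nor is 2 of 52 cycles a share of events: 52 is a ceiling, and Protocol Section 4.4 expects participation, including follow-up, to average about 12 to 18 months.

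**Conclusion.** The concern holds in a limited form. As defined, the by-term discontinuation table and the dedicated listing do not cover TEAEs that stop nivolumab in Group B from Cycle 3 on, whereas in concurrent groups they cover the whole of treatment. What is missing is the link between the adverse event term and the stop.

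The size is modest: one Phase 1 group under the current protocol, and four groups (B, E, G and K) as the SAP stands. With the SAP's four dose levels and 3 to 9 evaluable subjects per level, Group B has 4 × 3 = 12 to 4 × 9 = 36 evaluable subjects. The documents give no basis for the number of stops among them.

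The conclusion assumes that INCAGN01876 is not coded as withdrawn after its two planned doses. It has no bearing on the primary efficacy analysis or on any decision rule. It is worth correcting because the correction costs almost nothing and makes a tolerability display comparable across groups.

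**What to change.** - Reword the Section 8.2.5 bullet, Tables 3.2.15.1 and 3.2.15.2, and Listing 2.6.8 to cover TEAEs leading to discontinuation of any study treatment, and show which drug or drugs were stopped. This matches the scope of the interruption table.
- Add a row for any study treatment to the overall AE summary. The per-agent rows cannot simply be added up, because a subject whose drugs all stop together may be counted in more than one of them.
- State how the action on INCAGN01876 is to be read once its planned course in Group B is complete, so that the drug(s)-stopped entry does not depend on site habit.

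The cost is SAP wording and a changed selection in two tables, one listing and one summary row. No new data should be needed: the planned per-agent counts already require discontinuation to be known for each drug. That is an inference from those rows, since Protocol Section 8.1.2 mentions only the action taken with study drug. No dose or clinical management rule is touched.
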